Evaluation of Wire Electrodes to Activate the Expiratory Muscles to Restore
Cough / Sub-study to Spinal Cord Stimulation to Restore Cough

IRB08-00269/IRB98-00091

Title of Document: Study Protocol

Sub-study to Spinal Cord Stimulation to Restore Cough

IRB sub-study#: IRB08-00269

Date Approved: 7/21/2008

Study Protocol

Patients with cervical and thoracic spinal cord injuries often have paralysis of a major portion of their expiratory muscles and therefore, lack a normal cough mechanism (1). Consequently, most of these patients suffer from a markedly reduced ability to clear airway secretions, a factor which contributes to the development of recurrent respiratory tract infections (2,3). Since the spinal cord below the level of injury is intact in most patients, the motoneurons of the spinal cord and peripheral neuromuscular system innervating the expiratory muscles are intact. These muscles, therefore, can be electrically activated by electrical stimulation of the spinal roots to produce a functionally effective cough.

We have demonstrated that lower thoracic spinal cord stimulation (SCS), using disc electrodes, (4,5) has resulted in the generation of large positive airway pressures and peak expiratory flow rates, characteristics of a normal cough. Animal studies (performed in our laboratory) indicate that a similar response can be achieved using wire electrodes. Wire electrodes can be placed by less invasive surgical procedures, thereby reducing the surgical risks and post-operative care associated with implant of the disc electrodes. This methodology, therefore, has the potential to reach a larger population of spinal cord injured patients.

We plan to test the efficacy of temporary wire electrodes (6-8) in at least one and no more than eight study subjects enrolled in our current study ["Spinal Cord Stimulation to Restore Cough" (IRB98-00091)]. This will be done by temporarily placing the wire electrodes over the lower thoracic spinal cord. Stimulation will then be applied, and the degree of muscle contraction assessed by visual inspection and palpation over the abdominal wall and by recordings of expiratory airflow, expired volume and airway pressure. Since monopolar SCS with the disc leads, when applied in clinical trials, resulted in airway pressure generation that approximated pressures generated with a normal maximum cough, airway pressure generation achieved during SCS with these leads served as our gold standard to which all comparisons were made. If the response using the wire electrodes is similar to that of the disc electrodes, we can conclude that wire electrodes will offer an effective means of stimulation of the expiratory muscles to produce an effective cough.

Primary Aims:

To test the efficacy of wire electrodes to potentially replace disc electrodes currently being used under the IRB-approved study "Spinal Cord Stimulation to Restore Cough" (IRB98-00091).

Secondary Aims:

To determine if it is worthwhile to adapt the equipment currently in use under the IRB-approved study "Spinal Cord Stimulation to Restore Cough" (IRB98-00091) to mate with wire electrodes.

Sub-study to Spinal Cord Stimulation to Restore Cough

IRB sub-study#: IRB08-00269

Date Approved: 7/21/2008

REFERENCES

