Evaluation of Wire Electrodes to Activate the Expiratory Muscles to Restore
Cough / Sub-study to Spinal Cord Stimulation to Restore Cough

IRB08-00269/IRB98-00091

NCT number: 00995215

Date of the document: August 31, 2011

Title of Document: Statistical Analysis Plan

Sub-study to Spinal Cord Stimulation to Restore Cough

IRB sub-study#: IRB08-00269

Date Approved: 7/21/2008

Statistical Analysis Plan: The effects of spinal cord stimulation (SCS) with disc electrode and wire leads on airway pressure generation were compared. Airway pressure generation was compared for each electrode contact at each of the three spinal cord levels and in various combinations. Since monopolar SCS with the disc leads, when applied in clinical trials, resulted in airway pressure generation that approximated pressures generated with a normal maximum cough, airway pressure generation achieved during SCS with these leads served as our *gold standard* to which all comparisons were made. Data were reported as mean \pm SE. Statistical analysis was performed using a repeated measures analysis of variance and paired t-test. A p value <0.05 was taken as indicative of statistical significance.

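### The protocol's conclusion rests on wire and disc responses being similar, but the SAP plans only tests for a difference, with no interval and no definition of similar

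*Protocol*

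**What the plan says.** The protocol (Study Protocol section, approved 7/21/2008) plans to test temporary wire electrodes "in at least one and no more than eight study subjects". The response is to be judged by inspection and palpation of the abdominal wall and by recordings of airflow, expired volume and airway pressure. The decision rule is that if the wire response "is similar to that of the disc electrodes, we can conclude that wire electrodes will offer an effective means of stimulation". The primary aim is "To test the efficacy of wire electrodes to potentially replace disc electrodes currently being used" in the parent study.

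The SAP ("Date of the document: August 31, 2011", written in the past tense) says that the effects of stimulation "with disc electrode and wire leads on airway pressure generation were compared". The comparison is made for "each electrode contact at each of the three spinal cord levels and in various combinations", with monopolar disc stimulation as the gold standard. Results are given as mean and SE. On testing it says: "Statistical analysis was performed using a repeated measures analysis of variance and paired t-test", and "A p value <0.05 was taken as indicative of statistical significance".

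Neither document says how similar is to be judged, plans an interval for the wire-minus-disc difference, names the unit of analysis, says which comparison carries the conclusion, or gives the number of subjects analysed.

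**The concern.** The conclusion and the analysis answer different questions. The protocol wants to conclude that wire does about as well as disc. A test at p<0.05 can show that the two differ. If it does not, it leaves open whether they are alike or whether the sample was too small to tell. With at most eight subjects, the second explanation cannot be set aside without an interval.

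The SAP also makes many comparisons across contacts, levels and combinations. Without a named contrast, the conclusion could rest on any of them.

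A secondary point is that the enrolment range starts at one subject. With the subject as unit, none of the planned inferential quantities exists there, and the plan has no descriptive fallback.

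At stake is how far a reader can trust a finding of similarity. It bears on the possible replacement of disc electrodes and, under Secondary Aims, on whether adapting the equipment is worthwhile.

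**Working it through.** The plan has no sample-size or power figure to reproduce.

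**Inputs from the documents:** n from 1 to 8 (protocol); paired t-test, repeated measures ANOVA, SE and a 0.05 level (SAP). Two-sided testing is assumed because the SAP does not say.

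**Inputs assumed for illustration:** an SD of the paired difference of 5, 10 or 20% of disc pressure; a 20% deficit; k=3 or 6 conditions in the ANOVA. None is a proposed margin.

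**Step 1. Error degrees of freedom, subject as unit.** Paired t-test: n−1. One-factor within-subject ANOVA: (n−1)(k−1).

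| n | Paired t | ANOVA, k=3 | ANOVA, k=6 |
|---|---|---|---|
| 1 | 0 | 0 | 0 |
| 2 | 1 | 2 | 5 |
| 3 | 2 | 4 | 10 |
| 8 | 7 | 14 | 35 |

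At n=1 every entry is 0 whatever k is, and the between-subject SE is undefined. From n=2 the methods can be computed.

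**Step 2. Precision.** The 95% CI half-width in SDs of the paired difference is t(0.975, n−1)/√n. For example, n=3 gives 4.303/1.732 = 2.48, and n=8 gives 2.365/2.828 = 0.84. Multiplying by the assumed SD gives a percentage of disc pressure.

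| n | Half-width (SDs) | SD 5% | SD 10% | SD 20% |
|---|---|---|---|---|
| 2 | 8.98 | 45% | 90% | 180% |
| 3 | 2.48 | 12% | 25% | 50% |
| 4 | 1.59 | 8% | 16% | 32% |
| 5 | 1.24 | 6% | 12% | 25% |
| 8 | 0.84 | 4% | 8% | 17% |

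**Step 3. What the interval could exclude.** If wire and disc are truly equal, the chance that the lower 95% limit lies above a 20% deficit comes from the noncentral t distribution, with standardised effect 20/SD = 4, 2 or 1.

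| n | SD 5% | SD 10% | SD 20% |
|---|---|---|---|
| 2 | 0.343 | 0.176 | 0.091 |
| 3 | 0.908 | 0.471 | 0.179 |
| 4 | >0.99 | 0.755 | 0.289 |
| 5 | >0.99 | 0.909 | 0.401 |
| 8 | >0.99 | 0.998 | 0.681 |

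**Step 4. What a non-significant test means.** If wire truly falls short by 20%, the chance of p≥0.05 is, for SDs of 5/10/20%: 0.657/0.824/0.907 at n=2, 0.092/0.529/0.821 at n=3, and <0.001/0.002/0.319 at n=8.

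So n=2 is weak throughout, and n=3 is informative only if the differences are very consistent between subjects. From n=4 upward the answer turns on the SD, which the documents do not give.

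**The case against.** The strongest reply has four parts.

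- **One subject may be hypothetical.** The range is an enrolment permission in a 2008 protocol. The SAP of 2011 reports in the past tense that means, SEs and tests were produced, which suggests, without proving, that more than one subject was analysed. A reader might infer that the planned analysis could not be run; the documents do not support that. This part stands, so the one-subject case is only a secondary point. Using contacts or repeat stimulations as replicates would give degrees of freedom at n=1, but the result would describe that one person only.
- **The SAP never equates p≥0.05 with similarity.** A reader might infer that it does; it does not say so. The protocol also lists inspection, palpation, airflow and volume, so similar may be meant as a broader physiological judgement. This stands too. What remains is that nothing links the only planned tests to the stated conclusion.
- **The stakes are modest.** The aim speaks of potential replacement, in a small sub-study of temporary electrodes. That is fair, but the protocol still says that effectiveness can be concluded.
- **The middle of the range is less bleak.** With assumed SDs of 5 or 10%, four or five subjects would exclude a 20% deficit with a chance of about 0.76 or more. So the figures do not show that the permitted number is too small.

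**Conclusion.** The concern holds as a mismatch between test and conclusion. At every permitted number the p<0.05 difference tests do not address the similarity rule, and the plan has no interval or criterion that does. This needs no assumed SD. Its practical size does. The half-width falls from 9.0 SDs at n=2 to 0.84 at n=8. Under the illustrative assumptions, a non-significant result would miss a true 20% deficit in 66 to 91% of trials at n=2 and in fewer than 1% to 32% at n=8.

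The zero degrees of freedom at n=1 are exact with the subject as unit, but conditional on a case that may not have occurred. The supported finding is narrower than either a failed analysis or a sample that is too small: the number analysed, the unit, the deciding contrast and the meaning of similar all need to be stated. It should be fixed, because the remedy uses data already needed for the planned paired t-test.

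**What to change.** In the SAP, or in the report if accrual is over:

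1. State the number of subjects analysed and how it was reached.
2. Average any repeat stimulations of a configuration within subject, so that the subject is the unit.
3. Name one wire-versus-disc airway pressure contrast, against the monopolar disc stimulation already stated as gold standard, that carries the similarity conclusion. Treat the other contact, level and combination comparisons as supportive.
4. Report the mean paired wire-minus-disc difference for that contrast with its 95% CI, beside the planned p-values.
5. Limit the similarity conclusion to deficits that the interval excludes, and do not rest it on p≥0.05.
6. If only one subject was completed, report the individual recordings descriptively, with no SE, p-value or general efficacy conclusion. At two subjects, show the individual recordings with the interval.

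If the contrast is named after the results are known, say so.

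The cost is a few sentences. The cap of eight and the planned tests stay, and no extra subjects or procedures are needed. The downside is that the general conclusion may not be available at very small n.

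### The plan concludes that wire electrodes work if their response is similar to disc, but it plans only tests of difference and commits to no interval for the within-subject wire-disc difference

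*Protocol*

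**What the plan says.** The protocol's decision statement opens with "If the response using the wire electrodes is similar to that of the disc electrodes, we can conclude that wire electrodes will offer". What it then concludes about wire is a claim of effectiveness: "an effective means of stimulation of the expiratory muscles to produce an effective cough". It comes just before the primary aim, which asks whether wire could replace disc. *Similar* is not defined.

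The reference is monopolar stimulation with disc leads: "airway pressure generation achieved during SCS with these leads served as our gold standard to which all comparisons were made". The SAP repeats that sentence and analyses airway pressure. The protocol also lists visual inspection, palpation, expiratory airflow and expired volume among the assessments, and its decision statement speaks only of the response. Airway pressure is therefore the best reading of the deciding measure, but the text does not fix it.

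The sample is given as "in at least one and no more than eight study subjects", with no derivation.

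On analysis the SAP says "Statistical analysis was performed using a repeated measures analysis of variance and paired t-test" and "A p value <0.05 was taken as indicative of statistical significance". On reporting it says "Data were reported as mean" ± SE, without saying whether the SE belongs to each electrode type or to the paired difference. Comparisons are made by contact, at three spinal levels and in various combinations. Neither document mentions a confidence interval, a margin or individual subject values.

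**The concern.** The decision statement needs evidence that wire is close to disc. Both planned tests take no difference as the null hypothesis, so a small p value speaks against similarity and a large one is silent. In a sample this small, a large p value can arise because the electrodes perform alike or because there are too few subjects to tell.

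The statement carries the primary aim. Wire might give somewhat less pressure than disc and still produce an effective cough, but the documents do not say how much less would be acceptable. The reader therefore needs the size of the difference and its uncertainty, and a p value gives neither. If the SE is reported separately for each electrode type, the precision of the paired difference cannot be worked out from those two SEs, because it depends on the within-subject correlation.

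**Working it through.** **Inputs from the documents.** One to eight subjects (protocol); wire and disc compared within subject by paired t-test, p<0.05 (SAP).

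**Assumptions.** Two-sided testing (sidedness is not stated); one wire-disc difference per subject; differences independent and roughly normal, which is hard to check at n≤8. The repeated measures analysis is not modelled, because its error structure and unit of analysis are not stated.

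**The plan's own figure.** The range of one to eight cannot be reproduced. No power, effect size, margin or SD of the paired difference is given.

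**Step 1: interval width.** The 95% half-width in sample SDs of the paired difference is t(0.975, n−1)/√n.

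| n | t(0.975, n−1) | Half-width (SDs) |
|---|---|---|
| 8 | 2.365 | 0.84 |
| 5 | 2.776 | 1.24 |
| 4 | 3.182 | 1.59 |
| 3 | 4.303 | 2.48 |
| 2 | 12.706 | 8.98 |
| 1 | none (0 df) | does not exist |

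At n=1 a test across contacts could be computed, but it would speak only to that subject.

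**Step 2: what p≥0.05 leaves open.** The half-width is also the largest observed mean deficit that is still non-significant. Multiplying it by an assumed paired SD, as a percentage of the disc mean, gives:

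| Assumed SD | n=8 | n=4 | n=3 |
|---|---|---|---|
| 10% | 8% | 16% | 25% |
| 15% | 13% | 24% | 37% |
| 25% | 21% | 40% | 62% |

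For example, 0.836 × 15% = 12.5% at n=8. The SDs are illustrative.

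**Step 3: how often a real deficit is missed.** Power comes from the noncentral t distribution with n−1 df and noncentrality (true difference/SD)×√n. For a true deficit of one paired SD, power is 68% at n=8 and 29% at n=4, so p≥0.05 occurs in 32% and 71% of studies. For half an SD, power is 23% and 11%, so it occurs in 77% and 89%.

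**The case against.** **The documents never equate p≥0.05 with similarity.** This is correct. A reader might infer that a non-significant test is the planned route to the conclusion, but neither document says so. A descriptive judgement is also open: the wire recordings could be set against a reference said to approximate a normal maximum cough. What stands is that no inferential support for the conclusion is planned.

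**The interval may be within reach already.** A paired t-test computes the mean difference and its SE. If the reported SE is that of the difference, the interval is one multiplication away. If both means and an exact paired p value are reported, the SE can be recovered as |difference|/|t| unless the difference is zero. So the documents do not support saying that the planned output must lack the interval. The gap is that nothing commits to reporting it.

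**This is a small sub-study of temporary electrodes with modest aims.** That rules out demanding more subjects or a formal non-inferiority trial. It does not excuse the decision statement, which goes beyond feasibility to a conclusion about effectiveness.

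**Every percentage rests on an assumed SD.** This is true. With tight pairing and eight subjects, non-significance would be fairly informative. Only the paired difference and its interval would show whether that case applies.

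**Conclusion.** The concern holds as a gap between the stated conclusion and the planned analysis, and it should be fixed. The planned tests can show a difference but cannot show that it is small. Over much of the permitted sample range the uncertainty is large: from 0.84 paired SDs either side of the mean at n=8 to 2.48 at n=3 and 8.98 at n=2, with nothing at subject level at n=1. These widths assume one independent, roughly normal difference per subject. They cannot be put into pressure units from the documents, and the percentages above show a range only.

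The finding does not show that the trial would misread a non-significant result, nor that wire is worse than disc.

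**What to change.** 1. For airway pressure, report each subject's wire and disc values and the subject-level mean paired difference (or log ratio) with its t-based 95% interval, naming the electrode configuration each refers to. Show airflow and volume in the same way as supporting data.
2. State that p≥0.05 is not evidence of similarity.
3. By default, present the results as descriptive feasibility data with no similarity conclusion. At n=1, report individual data only.
4. Optional, if a claim is wanted: when only the lower limit is used, call it not worse than disc by more than a margin; for *similar*, require both limits to lie within margins. Base the claim on one named decisive wire configuration, or acknowledge the selection across contacts, levels and combinations. The sponsor should justify the margin and label it post hoc if it was set after data were seen; the SAP is dated 2011 and written in the past tense.

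**Why one configuration matters.** If wire is truly at the margin, a single lower-limit check passes 2.5% of the time. If any one of several independent configurations may pass, the rate is 1 − 0.975³ = 7% for three and 1 − 0.975⁶ = 14% for six. Simulation at n=8 with an assumed correlation of 0.8 between configurations gives about 5% and 8%.

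**Cost.** Items 1 to 3 use the same subjects and data, and need only a paired calculation and changed wording. The downside is that more results will be reported as inconclusive at small n, and it falls mainly on item 4. As an illustration, take a 20% margin (assumed; nothing in the documents makes it the right one) and no true difference. The lower limit then clears the margin with probability 1 − F(t(0.975, n−1)), where F is the noncentral t distribution function with n−1 df and noncentrality (20/SD)×√n:

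| Assumed SD | n=8 | n=5 | n=3 |
|---|---|---|---|
| 10% | 99.8% | 91% | 47% |
| 15% | 90% | 61% | 27% |
| 25% | 50% | 28% | 13% |

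Requiring both limits to lie within margins would pass less often still.

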Evaluation of Wire Electrodes to Activate the Expiratory Muscles to Restore
Cough / Sub-study to Spinal Cord Stimulation to Restore Cough

IRB08-00269/IRB98-00091

NCT number: 00995215

Date of the document: August 31, 2011

Title of Document: Statistical Analysis Plan

Sub-study to Spinal Cord Stimulation to Restore Cough

IRB sub-study#: IRB08-00269

Date Approved: 7/21/2008

Statistical Analysis Plan: The effects of spinal cord stimulation (SCS) with disc electrode and wire leads on airway pressure generation were compared. Airway pressure generation was compared for each electrode contact at each of the three spinal cord levels and in various combinations. Since monopolar SCS with the disc leads, when applied in clinical trials, resulted in airway pressure generation that approximated pressures generated with a normal maximum cough, airway pressure generation achieved during SCS with these leads served as our *gold standard* to which all comparisons were made. Data were reported as mean \pm SE. Statistical analysis was performed using a repeated measures analysis of variance and paired t-test. A p value <0.05 was taken as indicative of statistical significance.

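### The SAP compares wire with disc across contacts, three levels and unlisted combinations, but neither document names the wire configuration that decides whether wire is similar to disc

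*SAP*

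**What the plan says.** The SAP has one analysis paragraph. It sets the outcome: "The effects of spinal cord stimulation (SCS) with disc electrode and wire leads on airway pressure generation were compared". It then sets the scope: "Airway pressure generation was compared for each electrode contact at each of the three spinal cord levels and in various combinations". The number of contacts is not given, the combinations are not listed, and no comparison is called primary. The methods are given in two sentences: "Statistical analysis was performed using a repeated measures analysis of variance and paired t-test" and "A p value <0.05 was taken as indicative of statistical significance". No adjustment is stated, nor whether the ANOVA must be significant before the t-tests are read.

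The Protocol and the SAP both make monopolar disc stimulation the reference: "airway pressure generation achieved during SCS with these leads served as our gold standard to which all comparisons were made".

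The decision is in the Protocol only, in the paragraph before Primary Aims. It is conditional: "If the response using the wire electrodes is similar to that of the disc electrodes", then wire may be concluded to be an effective means of stimulation. The primary aim is "To test the efficacy of wire electrodes to potentially replace disc electrodes currently being used". The sample is "in at least one and no more than eight study subjects". The secondary aim asks whether adapting the equipment is worthwhile.

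**The concern.** Many comparisons feed one conclusion, and nothing links the two. The Protocol speaks of the wire response as a single thing, while the SAP produces a set of wire responses of unstated size. The documents do not say whether similarity is judged on the best configuration, an average, a pre-chosen one or all of them.

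Mapping contacts and levels is sensible work for a small sub-study. The gap is that the mapping is not separated from the comparison that settles the primary aim. The same data could then support *different* by citing a comparison with p below 0.05, or *similar* by citing one without. A reader of the results could not tell a planned comparison from one picked after the mapping. At stake is the claim that wire can replace disc.

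**Working it through.** **No figure to reproduce.** The plan has no power or sample-size calculation. It gives three levels, the 0.05 threshold and one to eight subjects. Contacts, combinations, SD and correlations are not given.

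**Assumptions for the illustration.** n = 8, the best case. k = 3 (one contact per level) or k = 7 (three single levels, three pairs, one triple). Wire-minus-disc differences are normal with SD 1, so all sizes are in SDs of the paired difference. Tests are two-sided at 0.05. The correlation between differences is 0.5 to 0.9. The value 0.5 arises when all wire configurations share one disc reading with common variance σ² and covariance c: the covariance of two differences is σ² − c, each variance is 2(σ² − c), and the ratio is 0.5. If each level has its own disc reading, the correlation is not fixed by this argument, so the range remains an assumption.

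**Step 1: citing the best-looking configuration, equal true deficits.** The expected overstatement is E(k) × √((1 − ρ)/n), where E(k) is the expected maximum of k independent standard normals: E(3) = 0.846, E(7) = 1.352.
- ρ = 0.5: √(0.5/8) = 0.25, giving 0.21 (k = 3) and 0.34 (k = 7).
- ρ = 0.9: √(0.1/8) = 0.112, giving about 0.10 (k = 3) and 0.15 (k = 7).

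Simulation agrees. Equal deficits are close to the worst case, because the choice of best is then pure noise.

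**Step 2: the same, with true deficits evenly spaced from 0.9 to 1.5 SD.** By simulation, the chosen configuration is overstated, relative to its own true value, by about 0.01 (k = 3) to 0.07 (k = 7) at ρ = 0.9, and by about 0.1 to 0.25 at ρ = 0.5.

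**Step 3: a conditional calculation.** Suppose p ≥ 0.05 in any one configuration were read as similar. For one named comparison, the chance of non-significance comes from the noncentral t with 7 degrees of freedom and noncentrality d√8.

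| True deficit d (equal) | One named comparison | Any of 3 to 7, ρ 0.5 to 0.9 |
|---|---|---|
| 0.5 SD | 77% | can add at most 100 − 77 = 23 points |
| 1.2 SD | 17% | 25% to 53% |
| 2.0 SD | 0.2% | below 2% |

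At 1.2 SD the open family adds 8 to 36 points. At 2.0 SD it adds fewer than 2. At 0.5 SD most of the problem is already present with one comparison, because no similarity margin is stated.

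**Step 4: false differences.** With ungated t-tests and no true difference, the chance of at least one p < 0.05 is 9% to 25% over the same k and ρ, against 5% for one named test. An ANOVA gate (ρ = 0.5) lowers this to about 4%. If one configuration is truly worse by 1.2 to 2.0 SD, the gated rate among the others is 9% to 22%.

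**Step 5: what one named comparison would deliver.** The 95% CI half-width is t(0.975, n − 1)/√n times the observed SD of the differences: 2.365/√8 = 0.84 at n = 8, 1.05 at n = 6 and 1.59 at n = 4. At n = 1 there is no paired test or interval.

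**The case against.** The strongest reply is that this is a mapping study in a handful of people, that choosing the better configuration is partly legitimate when the question is whether wire could replace disc, and that the outcome and reference are already fixed. Much of this stands. Airway pressure and monopolar disc are fixed, and exploration is appropriate. But the Protocol goes beyond exploration to a stated conclusion, so the comparison behind it needs to be identifiable.

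Four stronger readings are tempting and should be resisted.

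- *The plan treats p ≥ 0.05 as similarity, or lets one favourable configuration suffice.* Neither document says so. They do not exclude it either, but Step 3 is conditional and also rests on an assumed deficit.
- *The disc comparator is wholly unspecified.* The SAP's reference to each of the three levels reads naturally as like-for-like matching. Only the matching for combinations is truly unstated.
- *Unadjusted testing favours wire.* A false difference counts against wire, and a multiplicity adjustment would make more comparisons non-significant. Step 4 is a secondary point.
- *The whole problem comes from the open family.* The missing similarity margin is a separate gap, and at small deficits it dominates.

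It is also fair that k and ρ are assumed and only n = 8 was simulated. The omission itself depends on none of these.

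**Conclusion.** The point holds as a limited one. The Protocol draws a single conclusion from an open set of comparisons, and no wire configuration is named as deciding it. What this adds, beyond the missing margin, is room for selection: about 0.10 to 0.34 SD of overstatement if configurations are equally deficient, and 0.01 to 0.25 SD if they differ, at n = 8 with three to seven comparisons and correlation 0.5 to 0.9. A rise from 17% to 25–53% in wrongly passing a 1.2 SD deficit applies only under a decision rule that the documents do not contain.

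The SAP is written in the past tense and dated August 31, 2011, against an approval date of 7/21/2008. A reader might infer that the deciding configuration was chosen after seeing the results. The documents do not show this; they only fail to show the contrary. The change should be made. Confidence is medium, because the size rests on assumptions.

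**What to change.** Name one wire configuration against monopolar disc at the matched level(s) as the deciding within-subject comparison. If it is a combination, state its disc counterpart. Report its mean paired difference in airway pressure with a 95% CI, and judge similarity by that interval against a largest acceptable deficit stated by the sponsor, not by p ≥ 0.05. State whether the ANOVA gates the t-tests. List every other contact, level and combination tested, and report each as an exploratory estimate with a CI.

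If the data had already been seen, the comparison cannot be made prospective. The remedy then reduces to disclosing when and how the deciding configuration was chosen, listing everything tested and labelling the conclusion exploratory.

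The cost is text and reporting only, with no new data. There are two drawbacks: fewer configurations can carry a claim, and an interval of ±0.84 observed SDs at n = 8, wider with fewer subjects, may leave similarity undecided.
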